2.9 Safety analyses

All safety analyses will be based on the safety set.

2.9.1 Adverse events (AEs)

AE summaries will include all AEs occurring during on treatment period. Additional summaries will be displayed to report all AEs, AEs related to study treatment, all SAEs and SAEs related to study treatment collected up to 150 days after last administration of LAG525/spartalizumab or up to 30 days after the last dose of carboplatin whichever comes last. All AEs collected in the AE eCRF page will be listed along with the information collected on those AEs e.g. AE relationship to study drug, AE outcome etc. AEs with start date outside of on-treatment period will be flagged in the listings.

AEs will be summarized by number and percentage of subjects having at least one AE, having at least one AE in each primary system organ class (SOC) and for each preferred term (PT) using MedDRA coding. A subject with multiple occurrences of an AE will be counted only once in the respective AE category. A subject with multiple CTCAE grades for the same preferred term will be summarized under the maximum CTCAE grade recorded for the event. AE with missing CTCAE grade will be included in the 'All grades' column of the summary tables.

In AE summaries, the primary system organ class will be presented alphabetically and the preferred terms will be sorted within primary SOC in descending frequency. The sort order for the preferred term will be based on their frequency in the LAG525 + PDR001 + carboplatin arm, then on their frequency in the LAG525 + PDR001 arm and LAG525 + carboplatin arm.

The following adverse event summaries will be produced by treatment arm: overview of adverse events (number and % of subjects with any AE, treatment-related AE, SAE, treatment-related SAE, fatal SAE, treatment-related fatal SAE, AE leading to discontinuation, treatment-related AE leading to discontinuation, AE leading to dose adjustment/interruption, AE requiring additional therapy), AEs by SOC and PT, summarized by relationship (all AEs and AEs related to study treatment), seriousness (SAEs and non-SAEs), leading to treatment discontinuation, leading to dose adjustment/interruption, requiring additional therapy, requiring immunosuppressive medication, requiring systemic corticosteroid (> 10 mg of prednisone or equivalent), and leading to fatal outcome. Concomitant medications with immunosuppressive intent and systemic corticosteroids (>10 mg of prednisone or equivalent) will be programmatically flagged using a pre-specified list from the clinical team.

In addition, a summary of serious adverse events with number of occurrences will be produced (an occurrence is defined as >1 day between start and prior end date of record of same preferred term). For the legal requirements of ClinicalTrials.gov and EudraCT at the time of the CSR for the final analysis, two required tables on on-treatment adverse events which are not serious adverse events with an incidence greater than 5% and on-treatment serious adverse events and SAE suspected to be related to study treatment will be provided by system organ class and preferred term on the safety set population.

If for a same subject, several consecutive AEs (irrespective of study treatment causality, seriousness and severity) occurred with the same SOC and PT:

- a single occurrence will be counted if there is ≤ 1 day gap between the end date of the preceding AE and the start date of the consecutive AE
- more than one occurrence will be counted if there is > 1 day gap between the end date of the preceding AE and the start date of the consecutive AE

For occurrence, the presence of at least one SAE / treatment-related SAE / non SAE has to be checked in a block e.g., among AEs in a ≤ 1 day gap block, if at least one SAE is occurring, then one occurrence is calculated for that SAE.

The number of deaths resulting from treatment-related SAEs and SAEs irrespective of study treatment relationship will be provided by SOC and PT.

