10.1 Definition of adverse events and reporting requirements

10.1.1 Adverse events

An adverse event (AE) is any untoward medical occurrence (e.g., any unfavorable and unintended sign [including abnormal laboratory findings], symptom or disease) in a participant or clinical investigation participant after providing written informed consent for participation in the study. Therefore, an AE may or may not be temporally or causally associated with the use of a medicinal (investigational) product.

The investigator has the responsibility for managing the safety of individual participant and identifying adverse events.

Novartis qualified medical personnel will be readily available to advise on trial related medical questions or problems.

The occurrence of adverse events must be sought by non-directive questioning of the participant at each visit during the study. Adverse events also may be detected when they are volunteered by the participant during or between visits or through physical examination findings, laboratory test findings, or other assessments.

Adverse events must be recorded in the Adverse Events CRF under the signs, symptoms or diagnosis associated with them, accompanied by the following information (as far as possible) (if the event is serious refer to Section 10.1.2):

1. The Common Toxicity Criteria (CTC) AE grade (version 5.0).

Adverse events will be assessed and graded according to the Common Terminology Criteria for Adverse Events (CTCAE) version 5.0.

2. its relationship to the study treatment. If the event is due to lack of efficacy or progression of underlying illness (i.e. progression of the study indication) the assessment of causality

will usually be 'Not suspected'. The rationale for this guidance is that the symptoms of a lack of efficacy or progression of underlying illness are not caused by the trial drug, they happen in spite of its administration and/or both lack of efficacy and progression of underlying disease can only be evaluated meaningfully by an analysis of cohorts, not on a single participant

- 3. its duration (start and end dates) or if the event is ongoing, an outcome of not recovered/not resolved must be reported.
- 4. whether it constitutes an SAE (see Section 10.1.2 for definition of SAE) and which seriousness criteria have been met
- 5. action taken with study treatment.

All adverse events must be treated appropriately. Action taken with study treatment may include one or more of the following:

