- Dose not changed
- Dose Reduced (only for carboplatin)
- Drug interrupted/withdrawn
- 6. its outcome
 - a. not recovered/not resolved;
 - b. recovered/resolved;
 - c. recovered/resolved with sequelae;
 - d. fatal; or unknown

If the event worsens the event should be reported a second time in the CRF noting the start date when the event worsens in toxicity. For grade 3 and 4 adverse events only, if improvement to a lower grade is determined a new entry for this event should be reported in the CRF noting the start date when the event improved from having been Grade 3 or Grade 4.

Conditions that were already present at the time of informed consent should be recorded in medical history of the participant.

Adverse events (including lab abnormalities that constitute AEs) should be described using a diagnosis whenever possible, rather than individual underlying signs and symptoms.

Adverse event monitoring should be continued for at least:

- 150 days following the last dose of LAG525 and/or spartalizumab
- until the start of a new post treatment antineoplastic medication if sooner than the 150 days mentioned above. If a participant starts a post treatment antineoplastic therapy, then only adverse events suspected to be related to study treatment should be collected out to 150 days after discontinuation of LAG525 and/or spartalizumab
- 30 days after discontinuation of carboplatin if the participant continued carboplatin more than 150 days after the last dose of LAG525 and/or spartalizumab.

Once an adverse event is detected, it must be followed until its resolution or until it is judged to be permanent (e.g. Continuing at the end of the study), and assessment must be made at each visit (or more frequently, if necessary) of any changes in severity, the suspected relationship to treatment, the interventions required to treat it, and the outcome.

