12.5.2 Safety endpoints

For all safety analyses, the safety set will be used. All listings and tables will be presented by treatment group.

Safety summaries (tables, figures) will include only data from the on-treatment period with the exception of baseline data which will also be summarized where appropriate (e.g., change from baseline summaries). In addition, a separate summary for death including on treatment and post treatment deaths will be provided. In particular, summary tables for adverse events (AEs) will summarize only on-treatment events, with a start date during the on-treatment period (treatment-emergent AEs).

The on-treatment period lasts from the date of first administration of study treatment to 30 days after the date of the last actual administration of any study treatment.

The overall observation period will be divided into three mutually exclusive segments:

- Pre-treatment period: from day of participant's informed consent to the day before first dose of study medication
- On-treatment period: from day of first dose of study medication to 30 days after last dose of study medication
- Post-treatment period: starting at day 31 after last dose of study medication.

If dates are incomplete in a way that clear assignment to pre-, on-, or post-treatment period cannot be made, then the respective data will be assigned to the on-treatment period. Additional details to address incomplete AE and/or dosing dates will be addressed in the SAP.

Adverse events

Summary tables for adverse events (AEs) will include only AEs that started or worsened during the on-treatment period, the *treatment-emergent* AEs.

Additional summaries will be displayed to report all AEs, AEs related to study treatment, all SAEs and SAEs related to study treatment collected up to 150 days after last administration of LAG525/spartalizumab or up to 30 days after the last dose of carboplatin whichever comes last.

The incidence of treatment-emergent adverse events (new or worsening from baseline) will be summarized by system organ class and or preferred term, severity (based on CTCAE grades), type of adverse event, relation to study treatment.

Serious adverse events, non-serious adverse events and adverse events of special interest (AESI) during the on-treatment period will be tabulated.

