In case time of assessment (e.g. pre-dose ECG) and time of treatment start is captured, the last available assessment before the treatment start date/time is used for baseline.

For safety parameters (e.g ECGs), where study requires multiple replicates per time point, the average of these measurements would be calculated for baseline (if not already available in the database).

In rare cases where multiple measurements meet the baseline definition, with no further flag or label that can identify the chronological order, then the following rule should be applied:

- If values are from central and local laboratories, the value from central assessment should be considered as baseline.
- If multiple values are from the same laboratory (local or central) or collected for ECGs or vital signs, then the value closest to normal should be considered as baseline.

If subjects have no value as defined above, the baseline result will be missing.

On-treatment assessment/event and observation periods

For adverse event reporting the overall observation period will be divided into three mutually exclusive segments:

1. **pre-treatment period:** from day of subject’s informed consent to the day before first administration of study treatment
2. **on-treatment period:** from date of first administration of study treatment to 30 days after date of last actual administration of any study treatment (including start and stop date)
3. **post-treatment period:** starting at day 31 after last administration of study treatment.

If dates are incomplete in a way that clear assignment to pre-, on-, post-treatment period cannot be made, then the respective data will be assigned to the on-treatment period. Refer to [Section 5.1.2](#) for imputation rules concerning AE start and stop dates.

For other safety data, the on-treatment period will start from the day after the date of first administration of study treatment, unless the time of assessment and time of treatment start is available on the day of study treatment start. For data where time of assessment (e.g. ECGs) and time of treatment start are captured, data collected on the day of first administration of study

treatment at a time before (after respectively) the time of first administration of study treatment will be considered on the pre-treatment period (on the on-treatment period respectively).

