Safety summaries (tables, figures) include only data from the on-treatment period with the exception of baseline data which will also be summarized where appropriate (e.g. change from baseline summaries). In addition, a separate summary for death including on treatment and post treatment deaths will be provided. In particular, summary tables for adverse events (AEs) will summarize only on-treatment events, with a start date during the on-treatment period (*treatment-emergent* AEs). However, all safety data (including those from the post-treatment period) will be listed and those collected during the pre-treatment and post-treatment period will be flagged.

Additional summaries will be displayed to report deaths, all AEs, AEs related to study treatment, all SAEs and SAEs related to study treatment collected up to 150 days after last administration of LAG525/spartalizumab or up to 30 days after the last dose of carboplatin whichever comes last..

Last contact date

The last contact date will be derived for subjects not known to have died at the analysis cut-off using the last complete date among the following:

Table 2-1 Last contact date data sources

Source data	Conditions
Date of Randomization	No Condition
Last contact date/last date subject was known to be alive from Survival Follow-up page	Subject status is reported to be alive, lost to follow-up or unknown
Start/End dates from further antineoplastic therapy	Non-missing medication/procedure term.
Start/End dates from study treatment pages	Non-missing dose. Doses of 0 are allowed.
End of treatment date from disposition page at end of treatment	No condition.
Tumor (RECIST / iRECIST) assessment date	Result is not missing
Verification for treatment beyond RECIST1.1 PD	At least one non missing parameter value
Laboratory/PK/IG collection dates	Was sample taken? = 'Yes'.
Vital signs date	At least one non-missing parameter value
Performance Status date	Non-missing performance status
Start/End dates of AE	Non-missing verbatim term

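### The SAP's start-date rule for on-treatment AEs would count the improvement of a Grade 3-4 event that began before first dose as treatment-emergent, though few participants, possibly none, are exposed

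*SAP*

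**What the plan says.** **Selection of AEs.** SAP 2.9.1: "AE summaries will include all AEs occurring during on treatment period". SAP 2.1.1 makes this operational: "summary tables for adverse events (AEs) will summarize only on-treatment events, with a start date during the on-treatment period". The period runs "from date of first administration of study treatment to 30 days after date of last actual administration of any study treatment". Neither section compares a record's grade with that of an earlier record of the same event.

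**The protocol's description.** Protocol 12.5.2 has two wordings. Its general paragraphs give the same start-date rule as the SAP. Under its adverse events subheading it says that the AE tables "will include only AEs that started or worsened during the on-treatment period", and it then describes incidence in terms of events that are new or have become worse relative to baseline.

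**How AEs are recorded.** Protocol 10.1.1 defines AEs as occurrences "after providing written informed consent for participation in the study", so events with onset in screening are in the database. Conditions that predate consent go to medical history instead. On worsening: "If the event worsens the event should be reported a second time in the CRF noting the start date when the event worsens". On improvement, for Grade 3 and 4 events only: "a new entry for this event should be reported in the CRF noting the start date when the event improved from having been Grade 3".

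**Linking of records.** SAP 2.9.1 treats consecutive AEs with the same system organ class and preferred term, separated by no more than one day, as a single occurrence. That rule serves the count of occurrences. It gives the linked block no onset date and does not settle whether the block is treatment-emergent.

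**Declared changes.** SAP section 4 reports no change from the protocol's analyses.

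**The concern.** Worsening and improvement both generate a new CRF entry with a new start date, so a start date after first dose does not by itself show that anything began or became worse on treatment. If the SAP rule is applied to entries, a Grade 3 event that began in screening and fell to Grade 1 in the first week of treatment appears in the on-treatment tables through its Grade 1 entry. The protocol's started-or-worsened wording would leave it out.

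The tables exposed are the AE overview and the incidence by system organ class and preferred term. Two details could extend the effect. SAP 2.9.1 reports the maximum grade recorded for an event without limiting this to on-treatment records, so the pre-treatment Grade 3 or 4 could be shown as the on-treatment grade. And SAP 2.9.1.1 takes time to first AESI from treatment start to the first event, so for a qualifying term an improvement date could stand in as an onset date.

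**Working it through.** The documents give no figure that depends on this rule, so there is none to reproduce. The check applies both wordings to invented records and then bounds the effect.

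**1. Improvement example.** One participant, one preferred term, entered as Protocol 10.1.1 requires:

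| Record | Grade | Start (study day) | End (study day) |
|---|---|---|---|
| A | 3 | -7 | 5 |
| B | 1 | 6 | 15 |

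- Start-date rule (SAP 2.1.1): A starts before first dose and is excluded; B starts on day 6 and is included. Count = 1.
- Started-or-worsened rule (Protocol 12.5.2): B continues A (gap 6 - 5 = 1 day) at a lower grade, so nothing started or worsened. Count = 0.

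**2. Worsening control.** Same dates, Grade 1 then Grade 3. The start-date rule counts the second record, and so does the started-or-worsened rule. The two wordings part only on improvement.

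**3. Re-worsening case.** Grade 3 before first dose, Grade 1 on treatment, then Grade 2 on treatment. The last record is lower than the pre-treatment grade, but the event did become worse during treatment. A correction that compares only with the last pre-treatment grade (2 is not greater than 3) would drop it. Comparing with the record just before (2 is greater than 1) keeps it.

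**4. Size per affected participant.** The Amendment 4 summary in the protocol gives 20, 34 and 34 participants randomized to Arms 1, 2 and 3. Safety-set sizes are not given, so these are assumed denominators.

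- Arm 1: 1/20 = 5.0 percentage points.
- Arms 2 and 3: 1/34 = 2.9 percentage points each.

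These are ceilings. SAP 2.9.1 counts a participant once per category, so nothing is added if the same participant has another on-treatment event of that term.

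**5. Registry table of non-serious AEs.** SAP 2.9.1 applies a cut of incidence above 5%. One extra participant would move a term from 1/34 = 2.9% to 2/34 = 5.9%, or from 1/20 = 5.0% to 2/20 = 10.0%. Either step crosses the cut, but only for a term already at a count of one.

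**6. Who can be affected.** All of the following must hold:

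- onset after consent and before first dose, with screening assessments confined to 21 days (Protocol 8.1);
- Grade 3 or 4, and still so at first dose;
- the participant nonetheless meets Protocol 5.1 and 5.2, including ECOG 0 or 1, the laboratory limits, and the exclusions for residual toxicity of prior cancer therapy and for infection requiring systemic antibiotics;
- improvement to a lower grade is then recorded after first dose.

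The set need not be empty: inclusion criterion 8 can require a new tumor biopsy at screening, so a procedure-related event is possible. The documents give no rate from which to estimate the number.

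**The case against.** **The SAP follows the protocol.** A reader might infer that the SAP contradicts the protocol's definition. The documents do not support that: Protocol 12.5.2 contains the same start-date sentence. The inconsistency lies inside the protocol, and the SAP inherits one half of it.

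**The SAP speaks of events, not CRF records.** Protocol 10.1.1 calls the improvement entry a further entry for the same event, and SAP section 4 declares no departure from the protocol, so a programmer could still apply the started-or-worsened condition. This stands in part: miscounting is what the stated rule yields when applied to entries, not something the documents show was done. The programming specifications are not among them. But no sentence in the SAP tells the programmer to link the entries for this purpose.

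**The one-day gap rule already covers it.** It does not. It would join the two records, but it is written for counting occurrences and is silent on treatment-emergent status.

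**The case is rare and traceable.** This stands. The conditions are narrow, all AEs are listed with out-of-period records flagged, and no inferential analysis is planned for the close-out report. A reader might also infer a general overstatement of toxicity, or inflated SAE and AESI tables. The documents support neither. An SAE table is affected only if the improvement entry is itself flagged serious. An AESI table is affected only if the term qualifies, and a qualifying Grade 3 or 4 event before any dose is improbable because most AESI terms are immune-mediated or infusion events.

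**Conclusion.** The point holds as a minor gap in wording. Protocol 12.5.2 gives two descriptions of a treatment-emergent AE, the SAP keeps only the start-date one, and the CRF rule for improving Grade 3 and 4 events makes the two give different counts (1 against 0 in the example). The effect is at most 5.0 points in Arm 1 or 2.9 points in Arms 2 and 3 on one term's incidence per affected participant. This rests on randomized numbers as denominators and on the participant having no other on-treatment event of that term. The number affected cannot be derived from the documents; it is likely to be small and may be zero. The ORR conclusion does not depend on it.

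**What to change.** In SAP 2.1.1 and 2.9.1:

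- Link consecutive records of the same preferred term when the gap is one day or less, reusing the existing occurrence rule.
- Do not count an on-treatment record as treatment-emergent when it is only a lower-grade continuation of an event that began before first dose.
- Count the linked event if it first starts on treatment, or if any on-treatment record has a higher grade than the record immediately before it. This keeps an event that improves and then worsens again on treatment. The SAP should state this choice openly, because the protocol's comparison with baseline could be read the other way for such an event.
- Take the maximum grade from treatment-emergent records only.
- Keep improvement-only entries in the listings.

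The cost is a few sentences in the SAP and slightly more programming. No new data are needed.
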